2.5.3 Rescue medication

Rescue medication is not planned in this study.

2.6 Analysis of the primary objective

The primary objective of this study is to evaluate the overall safety of the DFX FCT formulation, as measured by frequency and severity of AEs and changes in laboratory parameters, in patients with transfusion-dependent thalassemia or MDS at very low, low or intermediate risk.

2.6.1 Primary endpoint

The primary variables are:

- treatment emergent AEs (TEAEs)
 - An AE is defined as treatment emergent if its onset date is on or after (≥) the first administration of study treatment within this study or events present prior to start of study treatment but increased in severity on or after (≥) the first administration of study treatment within this study but not later than 30 days after the last study treatment in this study (i.e. during the safety observation period, see Section 2.1 for definition).
- changes from baseline at Months 6 and 12 for the following laboratory assessments:
 - serum creatinine
 - creatinine clearance
 - ALT/SGPT
 - AST/SGOT
 - red blood cell (RBC)
 - platelets

• white blood cell (WBC)

2.6.2 Statistical hypothesis, model, and method of analysis

No hypotheses will be tested. All analyses will be descriptive in nature.

The incidence of any TEAEs overall and by severity will be summarized using frequency counts, percentages of patients, and 95% CIs for percentages obtained using Clopper-Pearson method.

Laboratory data will be summarized using descriptive statistics including 95% CI of the mean for raw values and absolute change from baseline at each visit (see Table 2-2 for time windows definition). Furthermore, mean and standard error (SE) values will be plotted over time (see Table 2-2 for time windows definition) for each of the laboratory parameters of interest (serum creatinine, creatinine clearance, ALT/SGPT, AST/SGOT, RBC, platelets, WBC total).

The analysis of the primary variables will be performed on the Safety Set.

2.6.3 Handling of missing values/censoring/discontinuations

No missing values will be imputed however missing partial AE dates will be imputed following the rules outlined in Section 5.1.1.

2.6.4 Supportive analyses

Overall AEs and selected laboratory parameters (serum creatinine and creatinine clearance) of the primary objective will be analyzed separately by the subgroups of interest outlined in Section 2.2.1.

2.7 Analysis of the key secondary objective

There is no key secondary objective for this study.

2.8 Analysis of secondary efficacy objective(s)

The secondary objective of this study is to evaluate the efficacy of DFX FCT on serum ferritin levels (decrease or maintenance, according to the individual therapeutic goal).

2.8.1 Secondary endpoints

The secondary variables are:

- serum ferritin level at baseline, Month 6 (Visit 10), and Month 12 (Visit 16)
- change from baseline in serum ferritin at Month 6 (Visit 10) and Month 12 (Visit 16)

It should be noted that the maximum serum ferritin provided by certain laboratories is 4500 ng/mL with values above 4500 ng/mL represented as ">4500". If there is an occurrence of ">4500", the site will record this value in the electronic data capture (EDC) system as 4500 ng/mL. For derivations and table summaries, the value of 4501 will be used; for listings this value will be shown as ">4500".

2.8.2 Statistical hypothesis, model, and method of analysis

No hypotheses will be tested. All analyses will be descriptive in nature.

Serum ferritin will be summarized using descriptive statistics of raw values, absolute change from baseline, and relative change from baseline at each visit (see Table 2-2 for time windows definition). The summaries will include n, mean with respective 95% CI, SD, minimum, Q1, median, Q3, and maximum.

The analysis of the secondary variables will be performed on the FAS.

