7.1.4 Discontinuation of study treatment

Patients may voluntarily discontinue from the study treatment for any reason at any time. If a patient decides to discontinue from the study treatment, the investigator should make a reasonable effort (e.g. telephone, e-mail, letter) to understand the primary reason for this decision and record this information in the patient's chart and on the appropriate eCRF

Page 43

pages. They may be considered withdrawn if they state an intention to withdraw, fail to return for visits, or become lost to follow-up for any other reason.

The investigator should discontinue study treatment for a given patient if, he/she believes that continuation would be detrimental to the patient's well-being.

Study treatment must be discontinued under the following circumstances:

- Pregnancy
- Unwillingness to comply with procedures as outlined in the study protocol, including unwillingness to comply with the prescribed study treatment
- Discovery of patient ineligibility
- Intake of prohibited medications
- AE(s)
- Abnormal laboratory value(s)
- Unsatisfactory therapeutic effect
- Protocol violation
- Subject withdrew consent
- Lost to follow-up
- Administrative problems
- Death

Patients who prematurely discontinue study treatment should undergo an EOT visit (Month 24) within 7 days from last dose, at which time all of the assessments listed for EOT visit will be performed.

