1.2 Study objectives and endpoints

The study objectives and related endpoints are detailed in the following table (Table 1-1).

Table 1-1 Objectives and endpoints

Objective	Endpoint
Primary	
To evaluate the overall safety of DFX FCT formulation in patients with transfusion-dependent thalassemia or MDS at very low, low or intermediate risk	Overall safety, as measured by frequency and severity of adverse events (AEs) and changes in laboratory values of interest i.e. serum creatinine and creatinine clearance*
Secondary	

Objective	Endpoint
To evaluate efficacy of DFX FCT on serum ferritin levels (decrease or maintenance, according to the individual therapeutic goal)	Absolute and relative change of serum ferritin level over time
* Schwartz et al 1987	

2 Statistical methods

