The study day for a baseline or post-baseline scheduled or unscheduled visit is defined as:

• Study day = (Date of visit) - (Date of baseline visit) + 1

For visits prior to baseline, the study day is defined as:

• Study day = (Date of visit) - (Date of baseline visit)

Date of baseline visit is the date of first administration of study treatment.

Change from baseline and relative change from baseline will only be summarized for patients with both baseline and post-baseline data for the relevant visit and will be calculated using the following formulae:

- Change from baseline = Post-baseline value baseline value
- Relative change from baseline (%) = $100 \times ([Post-baseline value baseline value] / baseline value)$

All data will be listed by center and patient number, unless stated otherwise.

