2.8.3 Handling of missing values/censoring/discontinuations

No missing values will be imputed.

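### Ferritin change is averaged only over patients with a value at each visit and no analysis addresses drop-out, so the monthly means may lean toward benefit if stopping for lack of effect is material

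*SAP*

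**What the plan says.** Serum ferritin is the only efficacy assessment. Its endpoint in SAP 1.2 is "Absolute and relative change of serum ferritin level over time". SAP 2.8.1 and Protocol 10.5.1 designate Months 6 and 12. SAP 2.8.2 describes the summary: "Serum ferritin will be summarized using descriptive statistics of raw values, absolute change from baseline, and relative change from baseline at each visit". It includes n and a mean with 95% CI, on the windows of Table 2-2.

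Three statements fix who is counted:
- SAP 2.8.2: "The analysis of the secondary variables will be performed on the FAS".
- SAP 2.1: changes "will only be summarized for patients with both baseline and post-baseline data for the relevant visit".
- SAP 2.8.3: "No missing values will be imputed".

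Protocol 7.1.4 lists "Unsatisfactory therapeutic effect" among the circumstances in which study treatment must stop. It gives no ferritin threshold. Early stoppers have an end-of-treatment (EOT) visit within 7 days of the last dose, and Protocol Table 7-1 marks ferritin at that visit but schedules none afterwards. SAP Table 2-2 has a separate EOT row, which uses that value or, failing that, the last earlier post-baseline value.

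**The concern.** Using the full analysis set does not protect the by-visit means, because a patient without a value leaves that visit's mean. If some patients stop because ferritin is rising, the later means are taken over those who did better, and the 95% CI is centred on that selected group.

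The ferritin-related rules are also asymmetric. Lack of effect is a reason to stop treatment. Under Protocol 6.3.1.3, ferritin below 500 ng/mL leads only to considering an interruption, so that patient stays in the visit schedule. The secondary objective asks whether ferritin falls or is maintained, and a mean that drifts downward through selection bears directly on that answer.

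**Working it through.** The plan states no drop-out rate, ferritin SD or expected change, so there is no planned figure to reproduce. All sizes below rest on assumptions.

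**1. Identity.** Let d be the fraction without a value at a visit. The all-patient mean is (1 - d) × mean(remaining) + d × mean(stopped). Therefore:

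available-case mean - all-patient mean = -d × [mean(stopped) - mean(remaining)]

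| d | stopped 500 ng/mL lower | stopped 250 higher | stopped 500 higher | stopped 1000 higher |
|---|---|---|---|---|
| 5% | +25 | -12.5 | -25 | -50 |
| 10% | +50 | -25 | -50 | -100 |
| 20% | +100 | -50 | -100 | -200 |
| 30% | +150 | -75 | -150 | -300 |

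The sign depends on who stops, which the documents do not say.

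**2. Simulation on the log scale.** Assumptions: true geometric mean change 0%; SD of individual log slopes 0.025 per month, constant over time; residual log SD 0.15; monthly values; hazard of leaving rises with the observed increase. Results from two runs of this set-up:
- Month 6: bias under 1%.
- Month 12: about -1% to -3%, with 8% to 12% lost in the first run.
- Month 24: -8%, -13% and -18% with 18%, 23% and 28% lost in the first run; about -6% to -17% in the second. Together, about -6% to -18%.
- Leaving unrelated to ferritin (29% lost): bias 0.

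To see what Month 24 requires, apply the identity to logs: ln(0.92)/(-0.18) = 0.46 and ln(0.82)/(-0.28) = 0.71. The slope SD at Month 24 is 24 × 0.025 = 0.60. Stoppers must therefore lie about 0.8 to 1.2 of these SDs above those remaining.

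**3. Second simulation, in ng/mL, at Month 12.** N = 58; true mean change 0; slope SD 60 ng/mL per month; measurement SD 250; unrelated drop-out 1% per month; from Month 3, an added monthly hazard once the change passes +500.

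| added hazard | n left of 58 | lost | bias (ng/mL) |
|---|---|---|---|
| 5% | 48.7 | 9.3/58 = 16% | -60 |
| 10% | 46.1 | 11.9/58 = 21% | -111 |
| 20% | 42.1 | 15.9/58 = 27% | -195 |

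More patients are lost by Month 12 here than in step 2. With unrelated drop-out only (1.5% per month), the bias is 0. With equal stopping for rises and falls (5% each), it is about -1. With stopping for falls only (10%), it is +114.

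**4. Does the EOT row repair this?** In step 3, a last-value summary taken at Month 12 was off by only -7 to -15 when stopping followed rises. But a true mean change of 0 leaves no trend to lose by carrying a value forward. With an assumed true decline of 40 ng/mL per month, the last-value summary was off by +26 to +29. The available-case mean was off by -29, -54 and -94 at the three hazards. The two err in opposite directions, and neither estimates change at a fixed time.

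**5. Would a model help?** In 40 simulated trials of 58 patients, a random intercept and slope model gave -0.8% at Month 24, against -10.6% for available cases and -0.9% in the full data. This recovery is partly built in: drop-out was generated as missing at random, and the data followed the model.

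**The case against.** The strongest objections, and what stands of each:

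- **Direction.** A reader might infer that the reported means are biased toward benefit as a matter of fact. The documents do not support that. Protocol 7.1.4 lists twelve circumstances, including adverse events, withdrawal of consent, administrative problems and death, and gives no frequencies. Steps 1 and 3 show that the bias can be nil or reversed. This objection stands, and the claim is conditional.
- **Lost data.** A reader might also infer that early stoppers' ferritin vanishes. It does not: the EOT value counts in the monthly window where it falls, and again in the EOT row. This stands, but that row does not correct the Month 6 and Month 12 means.
- **Time point.** The larger percentages belong to Month 24, a supplementary row. This stands.
- **Dose adjustment.** Protocol 6.3.1.3 provides for dose adjustment every 3 months on ferritin trends, whereas step 2 keeps each slope constant. In a re-run with a separate drop-out hazard, an assumed quarterly slope reduction for rising ferritin cut the Month 24 bias from -8.5 points (16% lost) to about -2 points (13% lost). This stands, so the figures in step 2 are on the high side in this respect.
- **Statistic.** The SAP reports arithmetic summaries, not geometric means. Under step 2, the full-data mean relative change at Month 24 is exp[0.5 × (0.60² + 2 × 0.15²)] - 1 = +22%. In the 16%-lost run the available-case mean was still +9%. The bias is downward, but that statistic would not show an apparent improvement.
- **Redundancy.** SAP 2.8.2 already includes n, and SAP 2.4.1 already displays reasons for premature study discontinuation. Neither needs to be requested.

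**Conclusion.** The concern holds in conditional form. The monthly ferritin changes are available-case, nothing in the SAP addresses drop-out, and one listed stopping reason is tied to the endpoint. The means may therefore look too favourable if stopping for lack of effect is material.

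On the log-scale assumptions, with true geometric mean change 0% and stopping that follows rising ferritin, the bias is under 1% at Month 6, about -1% to -3% at Month 12 and about -6% to -18% at Month 24. The ng/mL assumptions, with heavier early loss, give -60 to -195 ng/mL at Month 12, so size is sensitive to inputs that the documents do not supply. Quoting the Month 24 range as the error in the designated endpoint would go beyond the documents.

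The analysis is descriptive and secondary in a study whose primary objective is safety. No test, type I error or power figure is affected. What is at risk is a misleading estimate and interval, which makes this a worthwhile improvement and not a fatal defect.

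**What to change.** Keep the planned observed-case table. Add to SAP 2.8.2:

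1. A supportive mixed model on log serum ferritin, using all visits with baseline as one of the responses. Use a parsimonious covariance (for example random intercept and slope) suited to at most 58 patients, and state in advance how time enters, because a separate effect for each visit may be too many. Report the geometric mean change with 95% CI at Months 6, 12 and 24.
2. EOT change shown separately for completers and early discontinuers.

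The data are already scheduled: Visits 3 to 28 give 28 - 3 + 1 = 26 ferritin values per completer. The model needs no explicit imputation, so it is compatible with SAP 2.8.3.

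The cost is SAP wording and supportive output. Two limitations should be stated. The model assumes missing at random, which the data cannot confirm. And SAP 2.8.1 sets values above 4500 ng/mL to 4501, which affects the high-ferritin patients at issue, so treat those values as censored or check sensitivity to them.

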2.8.3 Handling of missing values/censoring/discontinuations

No missing values will be imputed.

2.9 Safety analyses

The safety evaluations during the study will be summarized for the Safety Set, unless otherwise specified.

No inferential tests for differences in safety analyses will be performed.

2.9.1 Adverse events (AEs)

All AEs occurring before first administration of study treatment in this study will be assigned to the pre-treatment period and those occurring after last drug intake + 30 days will be assigned to the follow-up period (for listings only). Only TEAEs will be summarized.

AEs will be coded by primary SOC and PT according to the MedDRA dictionary (version 19.1 or a more recent version).

The following AE summaries will be presented:

- AEs, regardless of study drug relationship
- AEs by maximum severity grade (mild, moderate, severe), regardless of study drug relationship
- AEs, suspected to be related to the study treatment
- serious AEs (SAEs), regardless of study drug relationship
- AEs leading to study drug discontinuation, regardless of study drug relationship
- AEs requiring study drug dose adjustment or interruption, regardless of study drug relationship
- AEs requiring additional therapy, regardless of study drug relationship

In addition an overall summary of type of AEs (e.g. serious, leading to study drug discontinuation, requiring dose adjustment or/and interruption) will be presented overall and by maximum severity grade. An overall summary of AEs will also be presented overall and by maximum severity grade using frequency and percentage of patients along with 95% CIs for percentages obtained using Clopper-Pearson method.

AEs will be summarized by presenting the frequency and percentage of patients having at least one AE, and having at least one AE by primary SOC and/or PT, severity, and relationship to

study drug by treatment group. A patient with multiple occurrences of an AE will be counted only once in the AE category.

For the legal requirements of clinicaltrials.gov and EudraCT, two required tables on TEAEs which are not SAEs with an incidence greater than 5% and on treatment emergent SAEs and SAEs suspected to be related to study treatment will be provided by primary SOC and PT.

If for the same patient, several consecutive AEs (irrespective of study treatment causality, seriousness and severity) occurred with the same primary SOC and PT:

- a single occurrence will be counted if there is ≤ 1 day gap between the end date of the preceding AE and the start date of the consecutive AE
- more than one occurrence will be counted if there is > 1 day gap between the end date of the preceding AE and the start date of the consecutive AE

For occurrence, the presence of at least one SAE/SAE suspected to be related to study treatment/non-SAE has to be checked in a block e.g., among AEs in a \leq 1 day gap block, if at least one SAE is occurring, then one occurrence is calculated for that SAE.

In addition exposure-adjusted AE incidence will be presented by PT. It is defined as:

(Number of patients with new or worsened AEs during the on - treatment period) (Total number of days a patient is on treatment summed over all patients / 365.25)

Furthermore, all AEs (AEs during the pre-treatment period, TEAEs, AEs during the follow-up period) will be listed by center and patient number for the FAS. This will also include details of the AE (e.g., verbatim given by the investigator as well as the primary SOC and PT), onset date, end date, severity, and relationship to study treatment.

2.9.1.1 Adverse events of special interest/grouping of AEs

Specific groupings of AEs of special interest (AESI) will be considered and the number of patients with at least one event in each grouping will be reported. Such groups consist of AEs for which there is a specific clinical interest in connection with DFX treatment or AEs which are similar in nature (although not identical). Note that certain AEs may be reported within multiple groupings.

All AESI groupings are defined through the use of PT, High Level Terms (HLT), primary SOC, Standardized MedDRA Queries (SMQ), Novartis MedDRA Queries (NMQ) or through a combination of these components. The MedDRA terms to be used are defined in an independent AESI search table which is located in the document management system in the 'CREDI Projects/I/ICL670A/Integrated Medical Safety' folder. The latest AESI search table will be used.

The AESI search table will be used to map reported AEs to the notable AEs groupings. The list of AESIs may be updated during the course of the trial based on accumulating safety data. Therefore the CSR will list the AE groupings used and provide a listing of the corresponding AESI search table.

AESIs will be summarized regardless of study drug relationship, by grouping and PT.

In addition, AESIs during the first 6 and 12 months of treatment during this study will be summarized regardless of study drug relationship, by grouping and PT.

2.9.1.2 Selected gastrointestinal TEAEs

The incidence of any gastrointestional TEAE as well as selected gastrointestional TEAEs will be summarized by using frequency and percentage of patients along with 95% CIs for percentages obtained using Clopper-Pearson method.

Selected gastrointestional AEs include the following PTs: diarrhoea, constipation, nausea, vomiting, and abdominal pain.

2.9.2 **Deaths**

The number and percentage of deaths resulting from SAEs suspected to be related to study treatment and SAEs irrespective of study treatment relationship will be provided by primary SOC and PT.

In addition, the primary and contributing reason for death will be listed for all deaths by center and patient number.

2.9.3 Laboratory data

Hematology, serum chemistry, and urinalysis parameters will be presented using standard international (SI) units and the severity grade calculated using the low/normal/high classifications based on laboratory normal ranges, and for selected parameters by notable/extended ranges.

Raw values as well as absolute and relative change from baseline values for hematology, biochemistry, and urinalysis laboratory parameters will be summarized descriptively by visit (see Table 2-2 for time windows definition).

The following summaries will be generated separately for hematology, biochemistry, and urinary laboratory tests:

- shift tables using normal/notable/extended ranges to compare baseline to the worst ontreatment value
- listing of all laboratory data with values flagged to show the corresponding normal/notable/extended ranges

All data, including data from unscheduled visits, will be considered when identifying abnormal values.

Shift tables based on normal ranges to compare baseline to the worst post-baseline value will be provided by parameter for hematology, biochemistry, and urinary laboratory data.

A similar shift table will be provided based on notable/extended ranges for key safety laboratory parameters defined in Section 10.5.2.2 (Clinical Trial Protocol CICL670AIC04 Amended Protocol Version 1, 25 October 2017).

2.9.4 Other safety data

2.9.4.1 ECG and cardiac imaging data

All data from ECG will be listed by center and patient number for the FAS. Patients with clinically significant abnormal interpretations or abnormal values will be flagged. A listing of patients with new or worsened clinically significant ECG abnormality compared to baseline will be provided.

2.9.4.2 Vital signs

Vital signs (sitting blood pressure [systolic blood pressure, diastolic blood pressure], weight, and BMI) will be summarized for the Safety Set using descriptive statistics, by visit for raw values and absolute change from baseline.

Clinically notable values for certain vital sign measurements are defined in Section 10.5.2.3 (Clinical Trial Protocol CICL670AIC04 Amended Version 1, 25 October 2017). The frequency and percentage of patients with clinically notable values values will be presented for the Safety Set.

Patient listings of vital signs data will be provided by center and patient number for the FAS. Values which are clinically notable will be flagged.

